1. JUSTIFICATION FOR THE STUDY

1.1. POSITIONING OF THE RESEARCH

With the increase in life expectancy among the French population, there has been a rise in the number of patients with fractures of the upper femur (FESF), particularly among the elderly. In France, the number of hospital stays for UEF has been increasing by 0.3% per year since 1998, and the incidence remains predominantly female. The crude incidence rate of UEF was 42.1/10,000 for people over 55 years of age in 2007. UEF mainly affects elderly and very elderly people. There has been a gradual increase in the average age of fracture patients. Again in 2007, patients over 80 years of age accounted for 60% of male patients operated on for FESF and 70% of female patients (1). This is a serious condition, with the risk of death increasing with age. It is 2% in women under 80 during hospitalisation, rising to 8.3% in those over 95. This mortality rate is higher in men, reaching 15% in men over 94 during hospitalisation (1). Longer-term mortality rates vary according to studies, from 14.7% at one year (2) to 46% at one year in patients over 90 years of age (3). However, there has been a gradual decrease in this mortality rate in France, probably due to improved surgical and perioperative care for patients (4).

Anaemia is common in the geriatric population. In a survey of a hospitalised geriatric population, 24% of patients had anaemia, the aetiology of which was iron deficiency in 15% of cases (5). It is also common in surgery, particularly in the perioperative period. In a study of 546 patients with fractures of the upper femur, 40.4% had anaemia on admission and 93.0% had anaemia postoperatively (6).

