2.1.2. Primary evaluation criterion

- Haemoglobin level on day 5 post-operatively (considered the post-operative haemoglobin reference level in this study)
 - In the case of patients who received a transfusion postoperatively, the reference haemoglobin level will be the haemoglobin level at the end of hospitalisation
- Change in the Activities of Daily Living (ADL) score pre-fracture and 6 months post-operatively.
A loss of independence will be defined as a decrease of one point or more in the ADL.

The reference value for haemoglobin levels was arbitrarily set at 5 days post-operatively. This is because haemoglobin levels recorded in A&E or on admission to the ward prior to surgery, or immediately post-operatively, may be influenced by factors other than isolated anaemia. Dehydration, present in the emergency department or on admission to the ward before the operation, corrected preoperatively, and postoperative haemodilution due to fluid replacement, cause the haemoglobin level to vary without there being any real deglobulation. We therefore postulate that the haemoglobin level on the 5th postoperative day can serve as a reference.

Confounding factors collected

All confounding factors related to loss of autonomy will be collected:

- Transfusion and number of red blood cell concentrates received

The indication for transfusion is at the discretion of the prescriber. However, it is generally accepted to transfuse patients with haemoglobin levels below 8 g/dL, or below 10 g/dL in cases of ischaemic heart disease or poor clinical tolerance.

- Age
- Gender
- Height, weight, Body Mass Index (BMI) calculation
- Screening for past or present higher brain function disorders
- Screening for major sensory disorders
- Screening for depressive symptoms: Mini Geriatric Depression Scale (MiniGDS)
- Comorbidities assessed using the Cumulative Illness Rating Scale - Geriatrics (CIRS-G)
- ASA score
- Number of medications (per class) taken by the patient (anticoagulants, antiplatelet agents, NSAIDs, anti-osteoporotic drugs, analgesics)

- Lifestyle and living environment
- Severe fractures before and after inclusion
- Other falls during the year
- Protein-energy malnutrition
- Iron deficiency (ferritin < 30 µg/L or CRP > 20 mg/L associated with a transferrin saturation coefficient < 15%)
- Recurrence of falls at 1, 3 and 6 months post-op

2.2. *SECONDARY OBJECTIVES AND EVALUATION CRITERIA*

2.2.1. *Secondary objectives*

The secondary objectives are to analyse:

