- the influence of post-operative anaemia:
 - on independence in elderly patients who have undergone surgery for a fracture of the upper end of the femur upon discharge from hospital, at 1 month and 3 months post-operatively
 - on mortality 6 months after surgery
- the progression of post-operative anaemia

2.2.2. *Secondary evaluation criteria*

- Lowest postoperative haemoglobin level recorded on admission to the emergency department, on admission to the ward, on D0 (day of surgery), D1, D3, D5, D10 and D15 (postoperative days).
The severity of anaemia will be defined as follows:
 - greater than 12 g/dL,
 - less than or equal to 12 g/L
 - less than or equal to 8 g/L
 - less than 8 g/dL (and therefore requiring a transfusion)
- Assessment of Activities of Daily Living (ADL): pre-fracture, on day 5 post-operative (or on discharge from hospital if discharged before day 5) at 1 month, 3 months and 6 months post-operative.
- Assessment of instrumental Activities of Daily Living (IADL): pre-fracture, at 1 month, 3 months and 6 months post-operative.
Loss of independence will be defined as a decrease of one point or more in the ADL and/or IADL.
- Vital status at 6 months post-operatively

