5.2.1. Description of methods planned planned, including the schedule for planned interim analyses

All variables collected will be described by minimum, maximum, quartiles, mean and standard deviation for quantitative variables and by number and percentage of each modality for qualitative variables.

Analysis of the primary endpoint:

The relationship between loss of independence at 6 months and post-operative anaemia will be analysed using a logistic model. If a link is found, a multivariate analysis will be performed to confirm the independence of the anaemia/independence relationship. To do this, all potential confounding factors will be tested in a univariate analysis. Factors associated with a p value <0.20 will be retained in the multivariate model.

Analysis of secondary criteria:

- The analysis of the relationship between loss of autonomy on day 5 (or on discharge from hospital if discharged before day 5), at 1 and 3 months, and post-operative anaemia will be performed using the same method as for the primary endpoint.
- The 6-month mortality rate will be estimated with its 95% confidence interval using the Kaplan-Meier method.

The association between anaemia and mortality at 6 months will be studied using a Cox proportional hazards model in order to take confounding factors into account.

- The progression of post-operative anaemia (D0 to D15) will be described graphically.

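### The mortality Cox model leaves its haemoglobin measure and time zero open, and the rule for transfused patients reads the exposure at a time that depends on survival

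*Combined protocol and SAP*

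**What the plan says.** - **Model.** Section 5.2.1 relates anaemia to 6-month mortality "using a Cox proportional hazards model in order to take confounding factors into account". It gives no time origin, landmark, delayed entry or time-dependent covariate, and does not say which haemoglobin value represents anaemia.
- **Time scale.** Section 2.2.1 sets the objective as the influence of anaemia "on mortality 6 months after surgery". Section 4.4 makes D0 the date of the procedure.
- **Reference exposure.** Section 2.1.2: "Haemoglobin level on day 5 post-operatively (considered the post-operative haemoglobin reference level in this study"). For patients transfused post-operatively, "the reference haemoglobin level will be the haemoglobin level at the end of hospitalisation".
- **A second candidate exposure.** The secondary criteria in section 2.2.2 begin "Lowest postoperative haemoglobin level recorded on admission to the emergency department" and list readings through to D15.
- **Missing data and analysis set.** Section 5.2.4 rules out imputation. Section 5.2.5 defines one analysis set, which needs autonomy recorded both before surgery and at 6 months.

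**The concern.** A Cox model needs the exposure to be known when a patient comes under observation. Here the clock appears to start at surgery, while the exposure is fixed days later. In transfused patients it is fixed on a day set by how long they stay and whether they survive. Two problems can follow, depending on how transfused patients who die in hospital are handled:

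- **Last value kept.** This is the most literal reading of the end-of-stay rule. The exposure is then a reading close to death, which the fatal illness may have lowered (reverse causation).
- **Value treated as missing.** With no imputation these deaths leave the model, and the transfused patients who remain are credited with a stay during which they could not have died (immortal time).

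Using the lowest value to D15 does not avoid the difficulty, because patients who live longer have more readings from which a minimum can be taken.

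Section 1.2.1 hopes to derive a management protocol that covers transfusion strategy. A spurious link between low haemoglobin and death that arises specifically among transfused patients would bear directly on that aim.

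**Working it through.** **Inputs from the documents.** 320 patients in 18 months, 210 per year, 10% mortality, 10% loss, 255 analysable, 6.3% cited 6-month mortality, 65% below 10 g/dL (all section 5.2.2). In-hospital mortality in women (section 1.1): "It is 2% in women under 80 during hospitalisation, rising to 8.3% in those over 95".

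**Inputs assumed, not in the documents.** Share of deaths occurring early or in hospital, share transfused, length of stay, and any fall in haemoglobin before death.

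**1. The plan's own figure.** 320 × 0.80 = 256; 320 × 0.9 × 0.9 = 259.2; 210 × 1.5 × 0.81 = 255.15. The stated 255 reproduces and is not in dispute. No power or event target is given for mortality.

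**2. Expected deaths and precision.** 320 × 10% = 32, or 320 × 6.3% ≈ 20. With 65% anaemic, SE(log HR) = √[1/(d × 0.65 × 0.35)], which is 0.37 for d = 32 and 0.47 for d = 20. The 95% limits are the HR divided and multiplied by about 2.1 or 2.5.

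**3. Deaths in hospital.** 320 × 2% = 6.4 and 320 × 8.3% = 26.6, or 20% and 83% of 32 deaths. These are rates for age subgroups of women, so they bound a range and do not estimate the share.

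**4. A common day-5 reading.** If nobody in the model dies before day 5, subtracting 5 days from every follow-up time leaves each risk set unchanged. Null simulations (400,000 patients, true HR 1; 15%, 30% or 50% of deaths in the first 15 days) gave identical HRs from surgery and from day 5: 1.001, 1.004 and 0.984. Only absolute mortality moves if it is estimated in day-5 survivors: 10.0% to 9.6%, 9.9% to 9.0%, 10.0% to 8.4%.

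**5. The other readings of the exposure.** Same simulation, true HR 1; 30% or 50% transfused, mean stay 8, 11 or 15 days in the second and third rows; Monte Carlo error up to about 0.035.

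| Reading | HR, clock from surgery | HR, clock from measurement or landmark |
|---|---|---|
| Transfused in-hospital deaths keep a last value 0.5 to 1 g/dL lower (anaemia HR) | 1.03 to 1.21 | 0.97 to 1.02 |
| Those deaths missing (anaemia HR) | 0.90 to 1.16 | 0.98 to 1.04 |
| Those deaths missing (transfusion HR) | 0.68 to 0.96 | 0.97 to 1.02 |
| Lowest value to D15 (anaemia HR) | 0.83 to 0.97 | 0.99 to 1.02 |

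In the second row the direction depends on whether transfused patients leave hospital less anaemic than the others (HR above 1) or more anaemic (HR below 1).

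**6. False positives at trial size.** 320 patients, 10% mortality, 35% transfused, last value kept, true HR 1, nominal 5%. Two separately coded simulations (400 and 1,000 runs per setting; the 20% row is from the second only):

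| Share of deaths in hospital | Fall of 1 g/dL | Fall of 2 g/dL |
|---|---|---|
| 20% | 7% | 10% |
| 50% | 13% | 30% to 35% |
| 80% | 24% to 26% | 67% to 71% |

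At 50% the HR per g/dL was 0.89 to 0.91 (1 g/dL fall) and 0.80 to 0.85 (2 g/dL fall). With no pre-death fall, false positives were 3% to 6%. A third coding gave 8% to 77% across falls of 1 to 2 g/dL.

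**7. Candidate remedies under the same null.** A day-5 landmark gave HR 0.99 to 1.01 and 4% to 7% false positives. If day 5 is itself the last reading before death and already falling, the landmark gave 8% to 20%. A simple time-dependent latest value gave 14% and 30% (half of deaths in hospital; 1 and 2 g/dL) and 22% and 60% (80% in hospital), so it keeps the reverse causation.

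**The case against.** The strongest reply is that section 5.2.1 does not commit the sponsor to any of this. It names no haemoglobin measure and no time origin. Surgery as origin is inferred from sections 2.2.1 and 4.4, and the day-5 or end-of-stay value is one of two candidates. That stands: the plan leaves the bias open and does not build it in.

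A reader might also infer that a day-5 exposure with the clock from surgery creates immortal-time bias for every patient. Step 4 shows that it does not. It only restricts the analysis to day-5 survivors, and a landmark loses those same early deaths. Nor do reverse causation and immortal time act together in the same patients, since they need opposite handling of transfused in-hospital deaths.

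The magnitudes rest on assumed inputs, and the 8.3% rate belongs to women over 95 while eligibility starts at 75. This is also fair.

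Finally, the analysis is secondary and unpowered. A distortion of up to about 20% in the HR (step 5) is smaller than the sampling error in step 2. This carries less weight, because bias does not shrink with sample size and the false-positive rate can already exceed 5% at 320 patients. Section 4.1 allows 42 months of inclusion. At an illustrative 210 × 3.5 = 735 patients, with half of deaths in hospital, false positives were 22% and 62% for falls of 1 and 2 g/dL.

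**Conclusion.** The concern holds in a limited form. The end-of-stay rule for transfused patients, combined with mortality counted from surgery and no landmark or delayed entry, can give a wrong answer in the mortality model under either handling of in-hospital deaths. The lowest value to D15 has its own immortal-time problem.

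The size cannot be fixed from the documents. Under the null, false positives run from about 5% with no pre-death fall to well above 10% when half or more of deaths occur in hospital after a fall of 1 to 2 g/dL. The in-hospital share, the fall and the transfusion rate are all assumptions. The documents do not support saying that the plan certainly produces this bias, or that the day-5 readings of untransfused patients are at fault.

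A connected gap is certain on a literal reading: the analysis set in section 5.2.5 requires recorded 6-month autonomy, which would remove the deaths from the mortality analysis altogether.

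This should be settled before analysis, with the weight due to a secondary objective.

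**What to change.** For the mortality analysis only:

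- Name the exposure and time zero in section 5.2.1.
- Use a day-5 landmark: patients alive at the landmark, follow-up from that day, and the day-5 haemoglobin for everyone, transfused or not. Accept readings within the ±2-day window and set the landmark no earlier than the reading (day 7 if the full window is used). Enter transfusion before the landmark as a covariate.
- Do not use the end-of-stay value or a simple time-dependent latest value as the main exposure.
- As a sensitivity analysis, exclude deaths in the first days after the landmark, because the landmark reduces reverse causation but does not remove it.
- Report deaths before the landmark descriptively, and keep the Kaplan-Meier estimate from surgery in all included patients.
- Define a mortality analysis set that does not depend on 6-month autonomy.

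**Cost.** No new data are needed: haemoglobin on D1, D3 and D5, transfusions and vital status are already collected (section 4.1). The change goes beyond SAP wording, because the mortality exposure would differ from the section 2.1.2 definition for transfused patients. Deaths before the landmark leave the Cox model.

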5.2.2. Statistical justification for the number of inclusions

According to data from the Medical Information Department (DIM) of the CHD in La Roche Sur Yon, over an inclusion period of 18 months, 320 patients aged over 75 underwent surgery on the upper end of the femur (210 patients per year, on average over the last 4 years of activity).

Assuming a mortality rate of 10% and a loss to follow-up rate of 10%, 255 patients could be analysed.

According to Gruson (20), 67.8% of patients regained their previous level of independence within 12 months, while 6.3% died within 6 months.

According to Halm (19), 65% of patients had post-operative anaemia of less than 10g/dL.

As the presence of at least 10 events (loss of independence) per criterion selected in the multivariate analysis is recommended, the inclusion of 255 patients appears to be consistent.

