Postoperative anaemia has multiple causes. It is probably aggravated by rehydration upon admission of patients with fractures (7). There is blood loss associated with the fracture and the formation of a haematoma prior to surgery (8), but also some postoperative occult bleeding: in 546 patients with a fracture of the upper end of the femur, Foss et al. showed that post-operative occult bleeding ranged from 547 to 1473 mL, in addition to the blood loss observed during surgery. Finally, there is a degree of acute inflammatory anaemia secondary to surgery. This inflammatory component is caused by a decrease in progenitor proliferation, a reduced red blood cell half-life and iron retention by macrophages. This retention is mediated by ferritin, which is then increased, and by hepcidin, a recently discovered protein that regulates iron metabolism (9).

Loss of independence, defined as a decrease in the ability to care for oneself, is also significant after a fracture of the upper end of the femur. Of 390 patients over the age of 65 who underwent surgery for an FESF and were analysed by Vochteloos team, nearly half did not regain their previous independence after one year. Only 25% of patients who were mobile without assistance regained their previous independence within three months of surgery. Nineteen percent of patients became bedridden. The most significant risk factors were a low level of previous independence and the occurrence of postoperative confusion (10).

The consequences of a loss of independence in elderly people are manifold (11). It leads to the intervention of outside help for activities of daily living, a change of living arrangements, a change in family relationships, and a risk of abuse by carers. The economic consequences are also significant:

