5.2.3. Expected degree of statistical significance

The significance threshold is set at 5%.

5.2.4. Method of unused or invalid data into account of missing,

No imputation will be performed on missing data. These will be described in terms of numbers and percentages.

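### The 255 patients are called consistent with 10 events per selected factor, but no events or model terms are counted and the p<0.20 screen that sets the model size has no cap

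*Combined protocol and SAP*

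**What the plan says.** Section 5.2.2 starts from 320 operated patients over 18 months at one hospital, deducts 10% for deaths and 10% for loss to follow-up, and arrives at 255 who can be analysed. It cites a study in which "67.8% of patients regained their previous level of independence within 12 months" and 6.3% died within 6 months. It then invokes ten events per selected criterion and concludes that this "is recommended, the inclusion of 255 patients appears to be consistent". It gives no event total, no number of criteria, and no power or detectable effect.

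The number of criteria is left to section 5.2.1. An unadjusted logistic model comes first, and "If a link is found, a multivariate analysis will be performed". For that second step all potential confounders are screened one at a time: "Factors associated with a p value <0.20 will be retained in the multivariate model". There is no maximum, no order of priority and no rule for a shortage of events.

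Section 2.1.2 supplies the candidates ("All confounding factors related to loss of autonomy will be collected") under 16 headings. It also defines the event: "A loss of independence will be defined as a decrease of one point or more in the ADL", measured from before the fracture to 6 months.

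**The concern.** A rule of ten events per factor can be checked only when both the events and the factors are known. Section 5.2.2 supplies neither, so its conclusion is asserted rather than shown, and nothing else in the section supports the size. The plan also lets the data decide how large the model becomes. The candidates were listed because they are thought to relate to loss of autonomy, so more of them should pass a lenient screen than chance alone would produce.

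At stake is the adjusted model, which is meant to confirm that the link between anaemia and independence is not explained by other factors. With too many data-selected terms for the events available, its haemoglobin estimate could be unstable. The analyses at day 5, 1 month and 3 months use the same method.

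**Working it through.** **The plan's own figure.** 320 × (1 − 0.10 − 0.10) = 256 and 320 × 0.9 × 0.9 = 259. From the yearly average, 210 × 1.5 = 315, and 315 × 0.9 × 0.9 = 255. The figure of 255 analysable patients reproduces.

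**Event rates available in the protocol.**
- Section 5.2.2: 1 − 0.678 = 32.2% not recovering at 12 months.
- Same sentence: 6.3% died within 6 months. If those deaths lie inside the 32.2% (the protocol does not say), 32.2 − 6.3 = 25.9% remain.
- Section 1.1: in another cohort, "nearly half did not regain their previous independence after one year". Taken as 50%, this is an optimistic upper bound only, for the reasons given below.

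**Terms supported.** Events = 255 × rate. Terms = the smaller of events and non-events, divided by 10 and rounded down. Haemoglobin is included in the count.

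| Rate | Events | Non-events | Terms | Events per term with 17 terms |
|---|---|---|---|---|
| 25.9% | 66.0 | 189.0 | 6 | 3.9 |
| 32.2% | 82.1 | 172.9 | 8 | 4.8 |
| 50% | 127.5 | 127.5 | 12 | 7.5 |

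Because 255 is already net of deaths, the low case can be rebased on survivors: 0.259 / 0.937 = 27.6%, or 70 events and 7 terms. This stays within the range of 6 to 8.

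**Terms the plan could ask for.** The 16 headings plus haemoglobin make 17 terms at one each. Several headings hold more than one variable: transfusion and units given; height, weight and BMI; five drug classes; fractures before and after inclusion; falls at three times. Seventeen is the count if every heading is kept at one term each, not a forecast.

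**How many might pass.** If no candidate were related to the outcome, 16 × 0.20 = 3.2 would pass on average. As an illustration only, assume independent screening with an equal chance of retention for each heading. The chance that 8 or more are kept (9 or more terms with haemoglobin, above the limit at 32.2%) is then 0.7% at a retention chance of 20%, 28% at 40%, 60% at 50% and 86% at 60%.

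**Coding of anaemia.** Section 5.2.1 does not say whether haemoglobin enters as a continuous value or in bands. Section 2.2.2 lists four severity levels. Four levels take three terms, leaving 8 − 3 = 5 or 6 − 3 = 3 for confounders.

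**Missing covariates.** Section 5.2.4 states: "No imputation will be performed on missing data". If 5% to 20% of patients lacked a retained covariate (an assumed range with no basis in the protocol), 242 to 204 patients would remain. At 32.2% that is 78 to 66 events, or 7 to 6 terms.

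**The case against.** The best defence is that the rule applies only to criteria actually selected. Keeping all 16 headings is improbable, and a handful of retained factors would satisfy the rule. The unadjusted first step meets it easily: 82 events for one term, or 27 per term for three. The adjusted model runs only if a link is found, and the protocol calls the rule a recommendation. All of this stands. It limits the point to a risk in one conditional model, but it does not show that the criterion is met.

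Several stronger readings are tempting, and the documents do not support them:

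- *The criterion is bound to fail.* That depends on how many factors pass and on the true event rate, and neither is known.
- *The figure of 255 is wrong, or the study must be enlarged.* The figure reproduces, and a shorter list can restore the rule. Equally, one cannot promise that no more patients are needed. If 255 were read as inclusions, the stated losses would leave 255 × 0.8 = 204 analysed, with 66 events and 6 terms at 32.2%. The derivation in the section favours the analysed reading.
- *The 50% rate shows that 12 terms are safe.* It is a one-year figure. Section 1.1 says that the studies it had cited to that point gave priority to walking, and the title of the reference concerns mobility.
- *A high enough event rate would accommodate all 17 terms.* By events alone, 170 / 255 = 66.7% would do. But only 85 non-events would then remain, and they would limit the model to 8 terms. With 255 patients the ceiling is 12 at any rate.
- *The 18-month, single-hospital accrual basis contradicts the 42-month multicentre design.* It is unexplained, but it is a separate clarification and adds no weight here.

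**Conclusion.** The point holds as a gap that is cheap to close, not as a fatal flaw. Section 5.2.2 draws a conclusion that its contents do not establish, and section 5.2.1 permits a model larger than the expected events support. On the section's own figures, 255 analysed patients support about 6 to 8 parameters in all, against 16 candidate headings plus haemoglobin. A breach of the protocol's criterion in the adjusted model is possible, not certain.

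This rests on 255 being the analysed number and on borrowed rates. Both cited rates are at one year rather than 6 months, and neither is stated to use a one-point ADL fall. The 67.8% comes from patients who, according to section 1.1, were independent beforehand, lived at home and were cognitively intact. This study also takes patients with dementia and nursing home residents. The rule of ten is applied because the protocol adopts it, not because it is endorsed here as a sample-size method. The omission itself is certain; the limits of 6 and 8 are only as good as those rates.

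**What to change.** In section 5.2.1, replace the p<0.20 screen with a confounder list chosen in advance on clinical grounds and set in priority order. Limit total parameters to the smaller of events and non-events divided by 10, counting every haemoglobin or anaemia term and every level of a multi-category factor. Plan for about 6 to 8. Extend down the list only if the observed event count allows, never because of the associations seen. State how haemoglobin will be coded.

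In section 5.2.2, restate the conclusion as the number of parameters that 255 analysed patients support: about 6 at 25.9% and 8 at 32.2%, with 12 at 50% as an optimistic bound. Say that the cited rates are not 6-month ADL rates, and that 255 is the analysed number, not the included one.

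The cost is wording and agreement on one list, with no new data to collect. The downside is that a shorter list leaves more room for residual confounding. If the investigators consider more confounders essential, a penalised model or a larger sample would be the alternatives to weigh.

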5.2.5. Selection of individuals to be included in the analyses

All patients for whom preoperative and 6-month loss of autonomy is recorded will be included in the analysis.

6. **MONITORING AND MANAGEMENT OF ADVERSE EVENTS**

6.1. ***DEFINITIONS***

Vigilance	This refers to the monitoring of medicines, medical devices and other health-related products. It also consists of prevention of the risk of adverse effects resulting from their use, whether this risk is potential or proven,
Adverse events (AE)	Any harmful event occurring in a person participating in research involving human subjects, whether or not the event is related to the research or the product being researched.
Adverse effects (AE)	An adverse event occurring in a person participating in research involving human subjects, when this event is related to the research or the product being researched.
Serious Adverse Effects/Events (SAE)/(SAE)	Any adverse effect/event that: 
 * results in death, * is life-threatening, * causes temporary or permanent incapacitation or disability, * requires or prolongs hospitalisation of the patient, * causes a congenital or neonatal abnormality, * is medically significant (the list of medically significant effects/events is defined by the EMA).
Unexpected adverse effects (UEAEs)	Any adverse effect whose nature, severity or progression is inconsistent with the information relating to the products, procedures and methods used during the research.
New information	Any new data that could lead to a reassessment of the benefits and risks of the research or the product being researched, to changes in the use of this product, in the conduct of the research, or in the documents relating to the research, or to the suspension, interruption or modification of the research protocol or similar research. For trials involving the first administration or use of a health product in people who do not have any medical conditions: any serious adverse effect.
Abuse	Intentional, persistent or sporadic excessive use of a drug that is accompanied by harmful physical or psychological reactions.
Overdose	Administration of a quantity of a drug, given in a single dose or cumulatively, that is above above the maximum recommended dose according to the rules of

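### Section 5.2.2 derives 255 as the number analysable after attrition, then justifies 255 as the number of inclusions, and gives no separate recruitment target

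*Combined protocol and SAP*

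**What the plan says.** Section 5.2.2 of the combined protocol and SAP, whose heading concerns the number of inclusions, proceeds in four steps.

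- It starts from one hospital's activity: "over an inclusion period of 18 months, 320 patients aged over 75 underwent surgery on the upper end of the femur", with the annual rate given as "210 patients per year, on average over the last 4 years of activity".
- It applies attrition: "Assuming a mortality rate of 10% and a loss to follow-up rate of 10%, 255 patients could be analysed".
- It cites outcome rates from an earlier hip-fracture cohort: "67.8% of patients regained their previous level of independence within 12 months, while 6.3% died within 6 months".
- It invokes a rule of thumb, that "the presence of at least 10 events (loss of independence) per criterion selected in the multivariate analysis is recommended", and concludes that "the inclusion of 255 patients appears to be consistent".

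Section 5.2.5 defines the analysis set: "All patients for whom preoperative and 6-month loss of autonomy is recorded will be included in the analysis". Section 5.2.4 rules out imputation. Section 4.1 sets a 42-month inclusion period and section 4.2 describes the study as multicentre; neither gives a number of patients to enrol.

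**The concern.** The figure of 255 is what remains once deaths and losses have been removed. The closing sentence of the same section then uses it as the number of inclusions. Elsewhere the protocol uses *inclusion*, when unqualified, for enrolment: the inclusion period and the 48-hour window in section 4.1, and the baseline measurements in section 4.3. A site, monitor or ethics committee looking for the recruitment target would find only 255.

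If 255 is enrolled, attrition applies to it. A patient who dies or is lost before the 6-month call has no 6-month ADL, is not imputed, and leaves the primary analysis. The section's only argument that the sample is adequate, the 10-events rule, would then rest on more patients than will be available. That margin matters because section 2.1.2 lists sixteen entries as confounding factors, and section 5.2.1 retains in the multivariate model any factor with p below 0.20.

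**Working it through.** **Inputs.** From 5.2.2: 320 operated patients in 18 months, or 210 per year; 10% mortality; 10% loss to follow-up; 255 analysable; at least 10 events per criterion; 67.8% recovered within 12 months and 6.3% died within 6 months in the cited cohort. From 5.2.4 and 5.2.5: no imputation, and both the pre-operative and 6-month records required.

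**Step 1: reproduce 255.** The section does not say whether the two 10% rates add or compound, so both are shown.

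| Pool | Additive (× 0.80) | Sequential (× 0.9 × 0.9 = 0.81) |
|---|---|---|
| 320 | 256 | 259.2 |
| 210 × 1.5 = 315 | 252 | 255.15 |

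All four results are close to 255, and 315 taken sequentially gives it almost exactly. So 255 is a post-attrition number.

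**Step 2: apply the same attrition to 255 enrolled.**

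- Additive: 255 × 0.80 = 204.
- Sequential: 255 × 0.81 = 206.6, about 207.

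**Step 3: enrolment needed for 255 analysable.**

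- Additive: 255 / 0.80 = 318.75, so 319.
- Sequential: 255 / 0.81 = 314.8, so 315.

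This agrees with the pool of 315–320 from which the section starts.

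**Step 4: expected events.** The protocol computes none, so the event rate is an assumption. The upper value is the complement of the cited recovery figure, 100 − 67.8 = 32.2%. The lower value also takes off the deaths: 32.2 − 6.3 = 25.9%. Re-expressing the lower value among survivors gives 25.9 / 93.7 = 27.6%, which lies inside the range.

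| Assumed rate | Events, 255 analysed | Parameters at 10 events | Events, 204 analysed | Parameters at 10 events |
|---|---|---|---|---|
| 32.2% | 82.1 | 8 | 65.7 | 6 |
| 25.9% | 66.0 | 6 | 52.8 | 5 |

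With 206.55 analysed the events are 66.5 and 53.5, and the parameter counts are unchanged.

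**Step 5: precision.** With standard errors proportional to 1/√n, the confidence-interval width ratio is √(255/204) = 1.118, or √(255/206.55) = 1.111. Intervals are about 11–12% wider.

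**The case against.** The strongest reply is that no calculation in 5.2.2 is wrong and that the concluding sentence concerns the multivariate analysis. On that reading *inclusion* means inclusion in the analysis, which is how section 5.2.5 uses the verb, and attrition is taken once only. The text also reads as a translation, and about 320 enrolled with 255 analysed is the likeliest intent. This has force: the point is an inconsistency of wording between enrolled and analysed, not a faulty sum. It does not remove the problem, because the section's heading and the rest of the protocol use the word for enrolment, and no figure of 315–320 is stated as the number to recruit.

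A reader might infer that recruitment will stop at 255 and leave the study a fifth short. The documents do not show that. Section 4.1 fixes a duration, not a count, and nothing sets 255 as a stopping point. At 210 patients per year, one hospital would operate on 210 × 3.5 = 735 patients in 42 months. The shortfall is therefore conditional on 255 being the enrolment target.

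A reader might also infer that power has been lost. The section states no power, effect size or precision target, so none is breached.

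It is fair, too, that the event rate is borrowed. The 67.8% is a 12-month recovery figure from another cohort, whereas this endpoint is a fall of one ADL point or more at 6 months. The event counts above are therefore illustrative.

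Finally, Appendix 1 (the protocol summary) is listed but was not in the text reviewed. A target stated there would settle the intent, though 5.2.2 would still have to agree with it.

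**Conclusion.** The inconsistency stands, at moderate severity. Section 5.2.2 gives one number two meanings, and it is the only sample size in the text available. If 255 are enrolled, about 204–207 are analysable, a loss of 19–20%. On an assumed event rate of 25.9–32.2%, that means about 53–66 events instead of 66–82, and 5–6 parameters instead of 6–8.

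This rests on three assumptions: that 255 is the enrolment number, that the section's own attrition rates hold, and that the cited cohort's rates carry over to this endpoint. If about 315–319 are in fact to be enrolled, the analysable number is as stated and only the sentence needs correcting.

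**What to change.** In 5.2.2, state two numbers separately: how many patients will be enrolled, and how many are expected to be analysable after deaths and losses. Base the 10-events check on the analysable number, with the assumed event rate and its source written down. Two versions are consistent with the section.

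- **255 analysable:** enrol about 315 (sequential attrition) to 319 (additive), and say which was used.
- **255 enrolled:** restate the analysable number as 204–207, with about 53–66 expected events at 25.9–32.2%.

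The 320 should not simply be relabelled as the target. It counts all operated patients at one hospital over 18 months, with no deduction for refusals or the exclusions in section 3.3, whereas section 4.1 allows 42 months and section 4.2 makes the study multicentre. Whichever target is chosen should match any figure in Appendix 1.

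The cost is a sentence or two. The first version changes nothing in the analysis if about 320 was always intended. The second makes the stated analysable figure less favourable and allows one or two fewer parameters in the multivariate model.
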